7.3.5 Early Termination Visit

- Record vital signs, results of physical examination
- Collect blood/urine for:
 - Hematology: CBC - hemoglobin, hematocrit, white blood cells (WBC) with differential count, platelet count; blood clotting tests: prothrombin time (PT), activated partial thromboplastin time (aPTT)

- Biochemistry: CMP - glucose, calcium, albumin, total protein, sodium, potassium, CO₂, chloride, BUN, creatinine, total bilirubin, alanine aminotransferase (ALT), aspartate aminotransferase (AST), alkaline phosphatase (ALP), lactate dehydrogenase (LDH); thyroid tests: (TSH and FT4)
- Urinalysis: UA with microscopic evaluation
- Serum pregnancy test
- Anti-double-stranded DNA (anti-dsDNA) antibody test
- Anti DNAse B Titer, Serum
- 40 mL of blood will be collected for research purposes in the laboratory of [name], including immune response evaluation.
- Tumor sample biopsy of injected lesion for histology and immune response assays
- Biopsy of non-target lesion (if applicable)
- Assessment and recording of ECOG Performance Status
- Assessment and recording of Tumor Burden (lesion measurements)
- Assessment and recording of Concomitant Medications
- Observation and recording of adverse or serious adverse events as defined by CTCAE v5.0
- CT as clinically indicated and/or PET scan (photographs may be utilized for melanoma confined to the skin)

7.3.6 Unscheduled Visit

- Record vital signs, results of targeted physical examination as indicated.
- Collect blood/urine/research biopsies as indicated, at the discretion of the Investigator.
- Assessment and recording of Concomitant Medications
- Observation and recording of adverse or serious adverse events as defined by CTCAE v5.0
- Assessment and recording of ECOG Performance Status

7.3.7 Schedule of Events Table

Schedule of Events Table

Schedule of Events: (Single dose cycle scenario)

Procedure	Screening (Day -36 to -1)	Week 0 (D=0)	Week 4** (D=28)*	Unscheduled visit	Early Termination Visit	Long-term Follow-up ¹
Informed consent eligibility	X					X
Physical exam w/vitals	X	X	X	X	X	
Medical history	X			X	X	X
Concomitant meds.	X	X	X	X	X	
AEs/SAEs	X	X	X	X	X	
IFx-Hu2.0 dosing		X				
Blood for Immune Response Evaluation		X	X	X	X	
***Clinical labs						
CBC, CMP	X	X	X	X	X	
LDH	X	X	X	X	X	
Blood clotting tests (PT/PTT)	X		X		X	
HLA typing (if not previously reported)		X				
EBV ab	X					
Hepatitis B and C, HTLV-1 & 2	X					
HIV, RPR (FTA if necessary)	X					
Thyroid Tests (Free T4, TSH)	X		X		X	
Serum Pregnancy Test	X	X	X		X	
Immunodeficiency Panel	X					
Urinalysis	X	X	X	X	X	
Anti-double-stranded DNA (anti-dsDNA)	X		X		X	
Anti-DNAse B Titer Serum	X		X		X	

ECG	X					
Optional Tumor sample/biopsies for immune response assays	X	X	X	X	X	
Optional Tumor sample/biopsies for histology	X		X	X	X	
CT and/or PET scan (Photographs may be utilized for melanoma confined to the skin)	X		X		X	
Performance Status	X	X	X	X	X	
Tumor Burden (lesion measurements)	X	X	X	X	X	
Confirmation of histology by Moffitt (may use archival tissue)	X					
Overall Survival						X

* +/-7 business days; **Final study visit; ***Screening labs may be performed within 7 days of treatment.

¹A long-term follow-up on 11/16/2020 (\pm 4 weeks) that includes the survival status and subsequent anti-cancer therapy since last being seen on trial will be obtained from the EMR. Subsequent therapies will be documented from the EMR for melanoma (immune-based therapy, chemotherapy, radiation, surgery) with clinical response if available.

Schedule of Events: (optional multiple dose cycle scenario, sample schedule for 3 cycles)

Procedure	Screening (Day -36 to -1)	Week 0 (D=0)	Week 4 (D=28)*	Week 7 (D=49)*	visit (21 days after last dose)	Unscheduled Visit	Early Term Visit	Long-term Follow-up ¹
Informed consent Eligibility	X							X
Physical exam w/vitals	X	X	X	X	X	X	X	
Medical history	X					X	X	X
Concomitant meds.	X	X	X	X	X	X	X	
AEs/SAEs	X	X	X	X	X	X	X	
IFx-Hu2.0 dosing		X	X	X				
Blood for Immune Response Evaluation		X	X	X	X	X	X	
***Clinical labs								
CBC, CMP	X	X	X	X	X	X	X	
LDH	X	X	X	X	X	X	X	
Blood clotting tests (PT/PTT)	X		X		X		X	
HLA typing (if not previously reported)	X							
EBV ab	X							
Hepatitis B and C, HTLV-1 & 2	X							
HIV, RPR (FTA if necessary)	X							
Thyroid Tests (Free T4, TSH)	X		X		X		X	
Serum Pregnancy Test	X	X	X	X	X	X	X	
Immunodeficiency Panel	X							

Urinalysis	X	X	X	X	X	X	X	
Anti-double-stranded DNA (anti- dsDNA)	X		X		X		X	
Anti-DNAse B Titer Serum	X		X		X		X	
ECG	X							
Optional Tumor sample/biopsies for immune response assays	X	X	X	X	X	X	X	
Overall Survival								X

* +/-7 business days; **Final study visit; ***Screening labs may be performed within 7 days of treatment.

¹ A long-term follow-up on 11/16/2020 (\pm 4 weeks) that includes the survival status and subsequent anti-cancer therapy since last being seen on trial will be obtained from the EMR. Subsequent therapies will be documented from the EMR for melanoma (immune-based therapy, chemotherapy, radiation, surgery) with clinical response if available.

7.4 Concomitant Medications, Treatments, and Procedures

All concomitant prescription medications taken during study participation will be recorded on the case report forms (CRFs). For this protocol, a prescription medication is defined as a medication that can be prescribed only by a properly authorized/licensed clinician. Medications to be reported in the CRF are concomitant prescription medications, over-the-counter medications, and non-prescription medications.

8 ASSESSMENT OF SAFETY

8.1 Specification of Safety Parameters

This study will comply with all applicable regulations on IND safety reporting requirements to the FDA in accordance with 21 CFR 312.32. This study will utilize CTCAE v5.0 for toxicity and AE reporting. All appropriate treatment areas at Moffitt Cancer Center have access to a copy of the CTCAE v5.0. Careful evaluation to determine the toxicity of IFx-Hu2.0 as a monotherapy will be performed. Adverse events will be documented beginning at initiation of treatment (Day 0) and continue at each visit detailed in the study treatment schema until progression, loss to follow-up, withdrawal of consent, or death. Subjects with treatment-related toxicity will be followed for the ongoing drug-related adverse events until resolved, return to baseline, deemed irreversible by the Moffitt treating physician, or until the subject is lost to follow up, withdrawal of study consent, removal of the subject from the trial by the Moffitt treating physician, or start of a subsequent anti-cancer therapy.

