4.2 Study Endpoints

4.2.1 Primary Endpoint

The primary endpoints of this trial will be the safety and feasibility of the treatment regimen. Safety will be reported using Common Terminology Criteria for Adverse Events (CTCAE) version 5.0. Feasibility will be defined as the ability to treat at least five of the six patients enrolled without dose-limiting toxicity (DLT).

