6.1.7 Starting Dose and Dose Escalation Schedule

The dose/lesion treated will be constant through this study: 100 µg of plasmid DNA per lesion injected at a final dose volume of 0.2 mL. However, depending on the subject, one, two, or three lesions would be injected at a time.

The subjects will receive IFx-Hu2.0 at a single time point as a monotherapy. These patients will then be observed for any dose-limiting toxicity or adverse events for up to four weeks. The maximum number of lesions to be injected in this study is three lesions.

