10.4.4 Planned Interim Analyses

10.4.4.1 Safety Review

The safety analysis will be conducted on the Safety Population. The following safety parameters will be evaluated: adverse events, clinical laboratory tests, physical examinations, vital signs, ECOG performance status, ECGs, radiographic or other imaging assessments, immune safety, and immunogenicity. All safety parameters will be summarized using descriptive statistics.

- **Adverse Events**

Treatment-emergent adverse events (TEAEs) are defined as signs or symptoms that emerge during treatment or within 30 days of the last dose of Investigational Product, including those signs and symptoms that have been absent pre-treatment or that have worsened relative to the pre-treatment assessment. Any adverse event considered related to treatment will also be considered a TEAE, regardless of the elapsed time since the last dose of Investigational Product.

An immune response AE, a subset of adverse events, is defined as a clinically significant AE of any organ that is associated with Investigational Product exposure of unknown etiology and is consistent with an immune-mediated mechanism.

All AEs recorded during the study will be summarized by cohort using descriptive statistics. The incidence of TEAEs will be summarized by body system, preferred term, verbatim of adverse event, intensity (based on CTCAE Version 5.0 grade), and relationship to the Investigational Product.

- **Vital Signs**

The observed vital signs at each visit and the change from baseline to each post-baseline visit will be summarized by cohort using descriptive statistics.

- **Physical Examination**

Abnormal findings in the physical examination will be summarized by dose cohort using descriptive statistics.

- **Clinical Laboratory Tests**

Clinical laboratory test values outside the normal range and clinically significant abnormal range will be flagged in the data listing. Laboratory data will be summarized by cohort using shift tables (baseline to notable post-baseline visit). The change from baseline will be summarized using descriptive statistics.

- **ECOG**

The data observed from ECOG performance status will be summarized appropriately.

- **Other Safety Evaluations**

The results of ECGs, radiographic or other imaging assessments, immune safety tests, and immunogenicity will be summarized appropriately.

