10.5 Sample Size

The intent of this study is to enroll six evaluable patients to assess the safety of IFx-Hu2.0 as a monotherapy. The sample size has the following precision for estimation of DLT rates for estimating ranging from 0.1 to 0.5. A DLT is defined as an adverse event equal to or greater than grade 3, definitely related to the investigational agent within a 4 week period. Precision is measured by 1-sided 95% upper confidence limit on the estimated DLT rate via exact binomial distribution. For example, if no DLT is observed in patients on IFX-Hu 2.0, then the true underlying DLT rate is lower than 0.393 with 95% confidence.

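### Section 8.1 ends adverse event documentation at progression, in conflict with section 8.3 and the 4-week DLT window, and no rule says how a patient with incomplete DLT observation is counted

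*Combined protocol and SAP*

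**What the plan says.** Section 8.1 opens adverse event (AE) documentation at Day 0 and has it "continue at each visit detailed in the study treatment schema until progression, loss to follow-up, withdrawal of consent, or death". The sentence after it extends follow-up only for drug-related toxicities already under way. It does not cover events that begin after progression.

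Other sections set windows that do not depend on tumour status:

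- Section 10.5 defines a DLT as an "adverse event equal to or greater than grade 3, definitely related to the investigational agent within a 4 week period".
- Section 6.1.7 has patients "observed for any dose-limiting toxicity or adverse events for up to four weeks", and section 7.1.2 has them assessed for four weeks before they move to other care.
- Section 10.4.4.1 counts as treatment-emergent (TEAE) the signs or symptoms that "emerge during treatment or within 30 days of the last dose of Investigational Product".
- Section 8.3 requires every AE during the study to be documented, whatever its relationship to treatment.

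Section 4.2.1 declares the regimen feasible if at least five of the six enrolled patients are treated free of DLT. The safety dataset in section 10.3 asks only for one dose. Section 10.5 says: "The intent of this study is to enroll six evaluable patients". The protocol does not define evaluable.

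**The concern.** A site that applies section 8.1 literally stops documenting new AEs once a patient progresses, even if the 4-week DLT window is still open. A non-serious grade 3 event that starts after that point could be missing from the DLT count. No minimum observation time is required, so the same patient could still count as DLT-free.

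The resulting error has one direction: an event that is not recorded can only make the treatment look safer. With six patients and a limit of one DLT, one missed event can change the feasibility conclusion.

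**Working it through.** **Which rule governs.** Set side by side, the sections do not settle the end of AE documentation:

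- Sections 8.3 and 7.1.2 point to full capture and conflict directly with 8.1.
- Section 6.1.7 leans the same way, but its four weeks are a maximum, so an earlier stop could be read into it.
- Section 5.4.2 asks for every effort at the safety follow-up that the protocol specifies, which leads back to whatever 8.1 specifies. It also concerns withdrawal or termination, and 5.4.1 does not list progression as a reason for either.
- The early termination visit (7.3.5) records AEs at that visit, not afterwards.
- The TEAE definition in 10.4.4.1 says what is analysed, not what the site must collect.

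**Whether progression can be declared before Day 28.** Section 5.3 anticipates progression as a reason to recruit further patients. Lesions are measured at unscheduled and early termination visits. The Week 4 visit may also fall 7 business days early. Ignoring holidays, 7 business days span 9 to 11 calendar days, so that visit can fall on Day 17 to Day 19, with 28 − 19 = 9 to 28 − 17 = 11 days of the DLT window left.

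**The plan's own figure.** Section 10.5 says: "Precision is measured by 1-sided 95% upper confidence limit on the estimated DLT rate via exact binomial distribution". For 0 events in n patients the limit is 1 − 0.05^(1/n).

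- n = 6: 1 − 0.05^(1/6) = 0.393, which reproduces the stated value.
- n = 5: 1 − 0.05^(1/5) = 0.451.
- n = 4: 1 − 0.05^(1/4) = 0.527.

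The last two apply only if one or two incompletely observed patients are left out and not replaced.

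**Effect on the 5-of-6 rule.** The rule passes with at most one recorded DLT. Assume independent patients with a common true DLT rate p.

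- All six fully observed: P(pass) = (1 − p)^6 + 6p(1 − p)^5. At p = 0.3 this is 0.1176 + 0.3025 = 0.420.
- One patient whose DLT risk is wholly missed but who counts as DLT-free: (1 − p)^5 + 5p(1 − p)^4 = 0.1681 + 0.3602 = 0.528.
- Two such patients: (1 − p)^4 + 4p(1 − p)^3 = 0.2401 + 0.4116 = 0.652.
- Half the risk missed: the affected patients have a recorded DLT rate of p/2 = 0.15. With one such patient, 0.85 × (0.1681 + 0.3602) + 0.15 × 0.1681 = 0.474. With two, 0.85² × (0.2401 + 0.4116) + 2 × 0.15 × 0.85 × 0.2401 = 0.532.

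Over the range of DLT rates named in section 10.5:

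| True DLT rate | Six observed | One, half missed | One, wholly missed | Two, half missed | Two, wholly missed |
|---|---|---|---|---|---|
| 0.1 | 0.886 | 0.902 | 0.919 | 0.918 | 0.948 |
| 0.2 | 0.655 | 0.696 | 0.737 | 0.737 | 0.819 |
| 0.3 | 0.420 | 0.474 | 0.528 | 0.532 | 0.652 |
| 0.4 | 0.233 | 0.285 | 0.337 | 0.346 | 0.475 |
| 0.5 | 0.109 | 0.148 | 0.188 | 0.199 | 0.312 |

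The numbers of affected patients and the missed fractions are assumptions. The documents give no rate of early progression.

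**The case against.** A reader might infer that a patient who progresses early will have later AEs unrecorded as a matter of protocol. The documents do not support that, because several provisions would catch many such events:

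- Section 8.3 asks at each visit about events since the last one. Progression is not a listed reason for withdrawal, so a patient who has progressed still has a Week 4 visit that records AEs.
- Grade 4 and 5 events are serious by definition, apart from a myelosuppression exception (8.1.2). All serious events go to the sponsor within 24 hours (8.4.2), with no stop at progression.
- Unexpected events are recorded throughout the study (8.3) and reported under 8.4.3. Section 2.3.1 reports no side effects with this product so far, so a definitely related grade 3 event would probably be unexpected. The investigator brochure is not available here, so that is likely rather than certain.
- Any AE considered treatment-related is a TEAE regardless of elapsed time (10.4.4.1), so it would be too much to say that the TEAE tables as a whole are cut short.

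The trigger is also narrow. The single-dose schedule has no planned visit between Day 0 and Week 4, so progression before then would surface mainly at an unscheduled visit, an early termination visit or an early Week 4 visit.

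All of this stands and limits the size of the problem. It does not remove it: section 8.1 still states a stopping rule that contradicts section 8.3, the safety routes start from an event the site has noticed and assessed, and nothing prevents an incompletely observed patient from counting as DLT-free.

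**Conclusion.** The point holds as an internal contradiction about when AE documentation ends, together with a missing rule for patients whose DLT observation is incomplete. It should be fixed, but it does not show that events will be lost. The main exposure is a new non-serious grade 3 event after a progression declared before Day 28.

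At an assumed true DLT rate of 0.3, one affected patient raises the chance of passing the feasibility rule by 5 to 11 percentage points, and two raise it by 11 to 23. The upper ends assume that the whole DLT risk of those patients is missed, so they are bounds; the serious and unexpected event routes would reduce them.

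A reader might also infer that the 0.393 limit is wrong and should be 0.451 or 0.527. It is not wrong: it is exact for six fully observed patients. The larger values need exclusion without replacement, and section 5.3 provides for two additional patients when existing ones progress, withdraw or are lost. If those restore six fully observed patients, 0.393 stands. Section 5.3 does not say whether the patient who progressed leaves the denominator.

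**What to change.** 1. Reconcile section 8.1 with section 8.3 by removing progression as an end point for AE documentation within the protocol's own windows. All new AEs would be recorded regardless of progression through 4 weeks after the first dose and 30 days after the last dose, unless consent is withdrawn or the patient dies or is lost to follow-up. Events after the start of another anti-cancer therapy would be recorded and flagged.

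2. In sections 4.2.1 and 10.5, state that a patient without complete 4-week DLT ascertainment and without a DLT is not counted as DLT-free. Such a patient is replaced under section 5.3, or the confidence limit is reported on the number fully observed. A patient who has had a DLT counts whatever the length of observation. This also covers loss to follow-up and withdrawal, which leave the same gap.

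The cost is a sentence in section 8.1 and a short rule in the statistical section. The visits already exist. Where the last visit falls before a window closes, a telephone call or chart check would be needed. Some of the additional AEs will be disease-related and will need attribution. Only data collection and counting change.

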8.1.1 Definition of Adverse Events (AE)

An AE is defined as any untoward medical occurrence associated with the use of an intervention in humans, whether or not considered intervention-related (21 CFR 312.32 (a)).

An ongoing or intermittent adverse event should be recorded only once, with the highest/worst grade reported for the event. This study will utilize the Common Terminology Criteria for Adverse Events version 5 (CTCAE v5) for toxicity

and adverse event reporting. A copy of the CTCAE v 5 can be downloaded from the CTEP home page <http://ctep.cancer.gov/reporting/ctc.html>.

8.1.2 Definition of Serious Adverse Events (SAE)

An adverse event or suspected adverse reaction is considered “serious” if, in the view of either the investigator or sponsor, it results in any of the following outcomes:

- death
- life-threatening
 - An adverse event or suspected adverse reaction is considered “life-threatening” if, in the view of either the investigator or sponsor, its occurrence places the patient or subject at immediate risk of death. It does not include an adverse event or suspected adverse reaction that, had it occurred in a more severe form, might have caused death.
- inpatient hospitalization or prolongation of existing hospitalization
- results in a persistent or significant incapacity or substantial disruption of the ability to conduct normal life functions

- a congenital anomaly/birth defect in the offspring of a subject
- Important medical events that may not result in death, be life-threatening, or require hospitalization may be considered serious when, based upon appropriate medical judgment, they may jeopardize the patient or subject and may require medical or surgical intervention to prevent one of the outcomes listed in this definition. Examples of such medical events include allergic bronchospasm requiring intensive treatment in an emergency room or at home, blood dyscrasias or convulsions that do not result in inpatient hospitalization, or the development of drug dependency or drug abuse.

For reporting purposes, also consider the occurrences of pregnancy or overdose (regardless of adverse outcome) as events which must be reported as important medical events. All Grade 4 and 5 adverse events are by definition serious, and must be reported within 24 hours of the site becoming aware of the event, with follow-up reporting of outcome with the exception of grade 4 and 5 myelosuppression (including anemia, neutropenia, and thrombocytopenia that does not require hospitalization).

8.1.3 Definition of Unexpected Adverse Drug Experience

An unexpected adverse drug experience (UP) is defined by the FDA as “any adverse drug experience, the specificity or severity of which is not consistent with the current investigator brochure. or, if an

investigator brochure is not required or available, the specificity or severity of which is not consistent with the risk information described in the general investigational plan or elsewhere in the current application, as amended”.

This study will use the FDA definition of UP.

8.2 Classification of an Adverse Event

8.2.1 Severity of Event

All AEs will be assessed by the clinician using NIH-NCI-DCTD-CTEP CTCAE v. 5.0, published: June 14, 2010.

For AEs not included in the protocol defined grading system, the following guidelines will be used to describe severity:

- **Mild** – Events require minimal or no treatment and do not interfere with the participant’s daily activities.
- **Moderate** – Events result in a low level of inconvenience or concern with the therapeutic measures. Moderate events may cause some interference with functioning.
- **Severe** – Events interrupt a participant’s usual daily activity and may require systemic drug therapy or other treatment. Severe events are usually potentially life-threatening or incapacitating.

8.2.2 Relationship to Study Event

The clinician’s assessment of an AE’s relationship to IFx-Hu2.0 is part of the documentation process, but it is not a factor in determining what is or is not reported in the study. If there is any doubt as to whether a clinical observation is an AE, the event should be reported. All AEs must have their relationship to study agent assessed. To help assess, the following guidelines are used.

- **Definitely Related** – There is clear evidence to suggest a causal relationship, and other possible contributing factors can be ruled out. The clinical event, including an abnormal laboratory test result, occurs in a plausible time relationship to study intervention administration and cannot be explained by concurrent disease or other drugs or chemicals. The response to withdrawal of the study intervention (dechallenge) should be clinically plausible. The event must be pharmacologically definitive, with use of a satisfactory rechallenge procedure if necessary.
- **Probably Related** – There is evidence to suggest a causal relationship, and the influence of other factors is unlikely. The clinical event, including an abnormal laboratory test result, occurs within a reasonable time after administration of the study intervention, is unlikely to be attributed to concurrent disease or other drugs or chemicals, and follows a clinically reasonable response on withdrawal (dechallenge). Rechallenge information is not required to fulfill this definition.
- **Possibly Related** – There is some evidence to suggest a causal relationship (e.g., the event occurred within a reasonable time after administration of the trial medication). However, other factors may have contributed to the event (e.g., the participant’s clinical condition, other concomitant events). Although an AE may rate only as “possibly related” soon after discovery, it can be flagged as requiring more information and later be upgraded to “probably related” or “definitely related”, as appropriate.

- **Unlikely to be related** – A clinical event, including an abnormal laboratory test result, whose temporal relationship to study intervention administration makes a causal relationship improbable (e.g., the event did not occur within a reasonable time after administration of the study intervention) and in which other drugs or chemicals or underlying disease provides plausible explanations (e.g., the participant's clinical condition, other concomitant treatments).
- **Not Related** – The AE is completely independent of study intervention administration, and/or evidence exists that the event is definitely related to another etiology. There must be an alternative, definitive etiology documented by the clinician.

